Annex D: List of Adverse Event

List of Adverse Event that should be recorded by the investigational sites in the EASiVENT Study.

Version 1.0 and its subsequent amendment, by reference only.

Remainder of page intentionally left blank.

Cover Page			
Study Title	EASIVENT Prospective, multicenter, randomized, controlled study comparing efficacy and safety of INTELLiVENT-ASV versus Non-automated Ventilation in adult ICU subjects.		
Study NCT number	NCT04400643		
Document	Statistical Analysis Plan		
Document version and Date	1.0 18 March 2022		

Statistical Analysis Plan

Sponsor:	Hamilton Medical AG
Protocol Title:	Prospective, Multicentre, Randomized, Controlled Study Comparing Efficacy and Safety of INTELLiVENT-ASV versus Non-automated Ventilation in adult ICU Subjects.
Study Code:	EASIVENT
Version:	1.0 of 18 March 2022

The signatures on this form indicate approval of this document.

L

Signature and Date

VERSION HISTORY

Version Date		Effective Date	Changes		
1.0	Draft version 05 Feb 2020	n/a	Initial version. Part of IDE submission		
	DRAFT version 13 May 2020	Was not released and	Alignment with protocol version 1.1 13 May 2020.		
		finalized, internal tracking.	Patient word replaced in the document to subject.		
		trucking.	Secondary endpoint is updated with Fio2 level assessment in both study arms.		
			VFD section is updated to clarify the 28D follow-up and definition of NIV is added.		
			Clarification added how to calculate VFD and when study ventilation will end.		
			Dropout definition is updated and expected number of % is added.		
			O'Brien-Fleming-Type method is added instead of Wang-Tsiatis. Sample sizes and operational characteristics for the trial using O'Brien Fleming boundaries for futility and efficacy is added.		
			Müller and Schäfer method is replaced by Following Mehta and Pocock (Mehta, 2011). Added to use the ITT population as the primary analysis population and the mITT for additional analyses.		
			Intervention period (Day 1 – Day 27) is updated to be aligned with CIP version 1.1.		
			Section 3.4 updated including changes in the sample size and enrolment cap added per site.		
			Clarification when the subject will exit the study is added in section 4.1.2 Participant Duration.		
			Section 4.2.2. DSMB is updated to be aligned with CIP version 1.1.		

		Section 4.4 Subgroup Definitions is updated with forest plots analysis implementation. Section 4.8 Methods to be Used for Handling missing data is updated to
		reflect the method of imputation.
		Section 8.4. Sensitivity Analyses and 8.5 Subset Analysis sections are added.
		Section 9.4 Adverse Events and Serious Adverse Event section is updated to be aligned with CIP version 1.1.
		9.6 Vital Signed, Physical Findings and Other Observations Related to Safety section is updated that the pivotal subjects' data during bedside training phase will not be taken into account for the study outcome and statistics.
		Appendix 1: updated to be in line with CIP version 1.1.
DRAFT version 13 APRIL 2021	Was not released and finalized, internal	Section 4.4 Additional subgroup analyses for the six ventilation and oxygenation variables
	tracking.	Section 9.2 Additional secondary safety variables added:
		 Severe Acute kidney injury (AKI) in need for CRRT/IHD Severe critical illness neuro- myopathy signs of tetraplegia affecting arms shoulder and neck with potential implication of respiratory muscle. Weakness is documented using the following score points: score 0 for no visible muscle contraction, score 1 for visible muscle contraction with no or trace movement, score 2 for

		 against gravity and score 3 for movement against gravity but not resistance. Severe critical illness encephalopathy leading to prolongation of mechanical ventilation. The most frequent causes being a metabolic or electrolyte disorder, systemic inflammation and other causes. Hypoxia, Stroke, intracranial bleeding, epilepsy and delirium. Encephalopathy is assessed using the GCS score and need to be reported is < 8 points. Withhold of weaning and/or withdrawal of mechanical ventilation because of treatment limitation related to patient wish or treatment futility due to irreparable single or multi-organ failure affect mechanical ventilation strategy, weaning from mechanical ventilation up to withdrawal of mechanical ventilation. Extubation failure that is related to weaning process by itself or associated conditions based on the interpretation of the investigator. Need for tracheostomy that is related to a difficult weaning process or associated conditions based on the interpretation of the investigator.
DRAFT version 13 of 16 th July 2021	Was not released and finalized, internal tracking.	Section 3.4 Inclusion CAP at each site changed to 15%. Section 4.4 Forest plots to report primary efficacy endpoints and some key secondary efficacy endpoints by regions.

			Section 6 Baseline characteristics by treatment and by region (EU and US)
	Draft 1 st October 2021	Was not released and finalized, internal tracking	Section 4.9: Changes to protocol Section 7.4: Other sensitivity analysis on the primary efficacy variable using ANCOVA model and adjusting for region. Section 7.6: Individual patient profiles plots for FiO2 and PEEP.

8.1 8.2 8.3 8.4 8.5 8.6 8.7 8.8	Extent of Exposure to Investigational Device Primary Safety Variable Secondary Safety Variable Tertiary Safety Variable Adverse Events and Serious Adverse Events Deaths Vital Signs, Physical Findings and Other Observations Related to Safety (Prior and) Concomitant Treatment	24 24 25 25 26 26 27
9. REF	ERENCES	28
10. LI	IST OF TABLES/GRAPHS/LISTINGS	29
10.1 10.2 10.3	List of Tables List of Figures List of Listings	29 32 33
APPEND	IX	34
Append Study /	dix 1 Summary of subject evaluation tests: schedule of assessments for both Arms	34

1. List of Abbreviations and Definition of Terms

Abbreviation	Term		
ADE	Adverse Device Effect		
AE	Adverse Event		
APRV	Airway Pressure Release Ventilation		
ARDS	Acute Respiratory Distress Syndrome		
ASADE	Anticipated Serious Adverse Effect		
ASV	Adaptive Support Ventilation		
ATC	Anatomical Therapeutic Chemical		
СР	Conditional Power		
CPAP	Continuous Positive Airway Pressure		
CRF	Case Report Form		
CTC	Common Toxicity Criteria		
DSMB	Data and Safety Monitoring Board		
ECCO2R	Extracorporeal Carbon Dioxide Removal		
ECMO	Extracorporeal Membrane Oxygenation		
EU	European Union		
FiO ₂	Fraction of Inspiratory Oxygen		
ICU	Intensive Care Unit		
IMDRF	International Medical Device Regulators Forum		
IMV	Invasive Mechanical Ventilation		
ITT	Intention-To-Treat		
MAR	Missing At Random		
MNAR	Missing Not At Random		
MV	Mechanical Ventilation		
NCI	National Cancer Institute		
NIV	Non-Invasive Ventilation		
PaO ₂	Partial Pressure of Oxygen		
PEEP	Positive End-Expiratory Pressure		
PetCO ₂	End-tidal partial pressure of carbon dioxide		
Pmax	Maximum Pressure		
PPLAT	Plateau Pressure		
RR	Respiratory Rate		
SADE	Serious Adverse Device Effect		
SAE	Serious Adverse Event		
SAP	Statistical Analysis Plan		
SBT	Spontaneous Breathing Trial		
SOFA	Sequential Organ Failure Assessment		
SpO2	Oxygen Saturation Measured by Pulse Oximetry		
US	United States		
USADE	Unanticipated Serious Adverse Device Effect		
VFD	Ventilator Free Day(s)		
VT	Tidal Volume		
WHO-DD	World Health Organization Drug Dictionary		

2. Introduction

This Statistical Analysis Plan (SAP) describes the statistical methodology and data handling for the clinical trial for Hamilton Medical AG with protocol number: EASiVENT_CIP_V2.0_clean_02OCT2020 (Prospective, multicenter, randomized, controlled study comparing efficacy and safety of INTELLiVENT-ASV versus Non-automated ventilation in adult ICU subjects).

The ICH guideline E3 "Structure and Content of Clinical Study Reports" and E9 "Statistical Principles for Clinical Trials", as well as E9 (R1) "Statistical Principles for Clinical Trials: Addendum: Estimands and Sensitivity Analysis in Clinical Trials" were used as guides to the writing of the plan.

This SAP is based on the following study document(s):

- Clinical Investigation Plan EASiVENT Version 2.0 of 02Oct2020
- Case Report Form, Version 6.0 of 07Jun2021

3. Study Design and Objectives

3.1 Study Objectives

3.1.1 Overall objective of the study

The study is designed to assess safety and efficacy of INTELLiVENT-ASV, a software accessory integrated in Hamilton ventilators that is designed to fully and automatically adjust both oxygenation and ventilation settings.

Efficacy and safety are primarily assessed to keep ventilation and oxygenation variables in optimal target ranges according to pertinent guidelines for Invasive Mechanical Ventilation.

3.1.2 Primary Objective

Efficacy: To assess the efficacy of INTELLiVENT-ASV in adult ICU subjects up to 7 days after enrolment.

Safety: To assess the safety of INTELLiVENT-ASV in adult ICU subjects up to 7 days after enrolment.

3.1.3 Secondary Objectives

The secondary objective is the assessment of ventilation safety and effectiveness by measuring physiologic parameters, clinical outcomes, associated interventions, workload, safety events and typical clinical complications up to day 28 after enrolment.

3.1.4 Tertiary Objectives

Efficacy: To assess the efficacy of INTELLiVENT-ASV in adult ICU subjects from day 8 up to day 28 after enrolment.

Safety: To assess the safety of INTELLiVENT-ASV in adult ICU subjects from day 8 up to day 28 after enrolment.

3.2 Study Endpoints

3.2.1 Primary endpoints

Primary endpoint will be measured continuously during the ventilation period up to 7 days after enrolment.

Efficacy

Efficacy of the investigational device will assess the ability to keep ventilation and oxygenation variables in optimal target ranges.

This endpoint will be determined by the percentage of time spent with six (6) variables in the optimal range during the 7 days after enrolment:

- 1) Tidal volume (VT)
- 2) Maximum pressure (Pmax)
- 3) Oxygen saturation measured by pulse oximetry (SpO₂)
- 4) End-tidal partial pressure of carbon dioxide (PetCO₂)
- 5) Respiratory rate (RR) for spontaneous breathing subjects
- 6) Pmax-PEEP for passive ARDS subjects

The optimal and sub-optimal ranges are defined by pertinent guidelines for different clinical conditions including normal lungs, brain injury, ARDS, and chronic hypercapnia. Please refer to Values for optimal, acceptable and sub-optimal ranges of the study protocol.

Safety:

The primary safety endpoint will be determined by percentage of time spent with at least one variable in the sub-optimal range during the first seven (7) days of enrolment. For the values of sub-optimal ranges, please refer toValues for optimal, acceptable and suboptimal ranges of the study protocol.

3.2.2 Secondary endpoints

Secondary endpoints will be recorded continuously until the end of intervention period (up to 28 days after enrolment).

Efficacy

Physiologic parameters:

- Respiratory mechanics (Compliance, resistance, expiratory time constant) will be assessed automatically breath-by-breath.
- Oxygenation (PaO₂/FiO₂, FiO₂, PEEP)
- Ventilation (VT, RR, mechanical power will be assessed automatically breath-bybreath, ΔP , P_{PLAT} , will be assessed twice a day).
- FiO₂ levels to be assessed in both study arms

Outcomes:

• Duration of invasive mechanical ventilation: time between intubation and last extubation or death. When a subject is re-intubated within 48 hours after extubation, the period between extubation and re-intubation is considered as invasive ventilation days.

- Duration of non-invasive mechanical ventilation: noninvasive ventilation refers to CPAP or pressure support NIV delivered before intubation or after extubation. High flow therapy is not considered in this calculation.
- Total duration of mechanical ventilation: sum of duration of invasive and noninvasive mechanical ventilation.
- Time from intubation to first successful Spontaneous Breathing Trial (SBT)
- Passive ventilation duration: passive ventilation is defined when the percentage of subject's triggered breath is lower than 25% of total respiratory rate.
- Weaning duration: time between the first sedation cessation to the last extubation or the last disconnection from the ventilator for tracheostomized subjects. Subjects re-intubated within 48h after extubation will be kept in the study. Subject re-intubated beyond 48h will be considered as weaned from the ventilation.
- VFD to day28 are defined as: the number of days from the time of initiating unassisted breathing to day 28 after start of ventilation, assuming survival for at least 48 hours and no re-intubation within 48 hours after initiating unassisted breathing and continued unassisted breathing to day 28.

NIV will be considered as assisted breathing. CPAP will not be considered as assisted breathing. Ventilator free days will be calculated separately for invasive ventilation support and any other ventilation support (invasive and noninvasive).

If a subject returns to assisted breathing (re-intubated within 48 hours) and subsequently achieves unassisted breathing to day 28, VFDs will be counted from the end of the last period of assisted breathing to day 28.

A period of assisted breathing lasting less than 24 hours and for the purpose of a surgical procedure will not count against the VFD calculation.

If a subject was receiving assisted invasive breathing on day 27 or dies prior to day 28, VFDs will be -1.

For subjects transferred to another hospital or other health care facility, study data collection will be stopped but subject will be contacted via a phone call on day 28 post enrolment to assess VFD endpoint if possible:

- ICU and hospital length of stay (discharge).
- ICU mortality (if the subjects is hospitalized in another hospital than the investigational site)
- Non-intensive ventilation (NIV) duration
- 28 days mortality
- Ventilation duration for study period (if re-intubated beyond 48h)
- Tracheostomy

Dropout could occur when patients are ventilated for less than 24 hours after inclusion because of unexpected death, transfer to another ICU, or withdrawal of informed consent. A maximum dropout rate of 5% of these cases is expected.

Associated interventions:

- Duration and doses of sedative infusion
- Duration and doses of analgesic infusion
- Duration and doses of vasopressors
- Duration and doses of myorelaxant
- Number of recruitment maneuvers
- Time spent in prone position
- Time spent with nitric oxide

Workload:

• Number of manual adjustments will be collected in both ventilation arms until considered as weaned from the ventilation.

Safety:

The secondary safety endpoint will be determined by evaluating the number of Serious Adverse Events (all SAEs included) within 28 days of the enrolment and the rescue therapy requirement (APRV, high frequency ventilation, ECCO2R and ECMO).

In addition, to better characterise the risk profile of the study population the following non-mechanical ventilation related adverse events will be recorded on study day 7 and 28.

- Severe Acute kidney injury (AKI) in need for CRRT/IHD
- Severe critical illness neuro-myopathy signs of tetraplegia affecting arms shoulder and neck with potential implication of respiratory muscle. Weakness is documented using the following score points: score 0 for no visible muscle contraction, score 1 for visible muscle contraction with no or trace movement, score 2 for limb movement but not against gravity and score 3 for movement against gravity but not resistance.
- Severe critical illness encephalopathy leading to prolongation of mechanical ventilation. The most frequent causes being a metabolic or electrolyte disorder, systemic inflammation and other causes. Hypoxia, Stroke, intracranial bleeding, epilepsy and delirium. Encephalopathy is assessed using the GCS score and need to be reported is < 8 points.
- Withhold of weaning and/or withdrawal of mechanical ventilation because of treatment limitation related to patient wish or treatment futility due to irreparable single or multi-organ failure affect mechanical ventilation strategy, weaning from mechanical ventilation up to withdrawal of mechanical ventilation.
- Extubation failure that is related to weaning process by itself or associated conditions based on the interpretation of the investigator.
- Need for tracheostomy that is related to a difficult weaning process or associated conditions based on the interpretation of the investigator.

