5.2 Secondary endpoints

Secondary endpoints will be recorded continuously until the end of intervention period (up to 28 days after enrollment).

Efficacy

Physiologic parameters:

1. Respiratory mechanics (Compliance, resistance, expiratory time constant) will be assessed automatically breath-by-breath
2. Oxygenation (PaO₂/FiO₂, FiO₂, PEEP)
3. Ventilation (VT, RR, mechanical power will be assessed automatically breath-by-breath, ΔP , P_{PLAT}, will be assessed twice a day).

4. FiO_2 levels to be assessed in both study arms

Outcomes:

1. Duration of invasive mechanical ventilation: time between intubation and last extubation or death. When a subject is re-intubated within 48 hours after extubation, the period between extubation and re-intubation is considered as invasive ventilation days.
2. Duration of non-invasive mechanical ventilation: noninvasive ventilation refers to CPAP or pressure support NIV delivered before intubation or after extubation. High flow therapy is not considered in this calculation.
3. Total duration of mechanical ventilation: sum of duration of invasive and noninvasive mechanical ventilation.
4. Time from intubation to first successful SBT
5. Passive ventilation duration: passive ventilation is defined when the percentage of subject's triggered breath is lower than 25% of total respiratory rate.
6. Weaning duration: time between the first sedation cessation to the last extubation or the last disconnection from the ventilator for tracheostomized subjects. Subjects reintubated within 48h after extubation will be kept in the study. Subject re-intubated beyond 48h will be considered as weaned from the ventilation.
7. VFD to day 28 are defined as: the number of days from the time of initiating unassisted breathing to day 28 after start of ventilation, assuming survival for at least 48 hours and no re-intubation within 48 hours after initiating unassisted breathing and continued unassisted breathing to day 28.

NIV will be considered as assisted breathing. CPAP will not be considered as assisted breathing. Ventilator free days will be calculated separately for invasive ventilation support and any other ventilation support (invasive and noninvasive).

If a subject returns to assisted breathing (re-intubated within 48 hours) and subsequently achieves unassisted breathing to day 28, VFDs will be counted from the end of the last period of assisted breathing to day 28.

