High flow nasal treatment, CPAP, and NIV can be used after extubation.

iv. Definition of unsuccessful extubation

If reintubation occurs within 48-hours of extubation, this event will be noted as a reintubation.

v. Completion of ventilator procedures.

Subjects will be considered to have completed the study ventilator procedures if any of the following conditions occur:

1. Death
2. ICU discharge
3. Subject or proxy withdraws consent

4. Principal investigator of site determines that the trial is no longer in the subject's best interest
5. Completed a period of 48 hours of unassisted breathing.

If a subject requires positive pressure ventilation after a period of unassisted breathing, these will be at the discretion of the team caring for the subject.

E. Tracheostomy

The following recommendations to be consider for Tracheostomy.

Tracheostomy will only be performed on strict indications and preferably not earlier than 10 days after intubation.

Indications for tracheostomy will be:

- Failure to intubate
- Expected duration of mechanical ventilation > 14 days
- Glasgow Coma Score < 7 and/or inadequate swallow or cough reflex with sputum retention
- Severe ICU-acquired weakness
- Prolonged or unsuccessful weaning
- Repeated respiratory failure after extubation

Readiness to wean criteria will be the same as intubated subjects. The weaning schedule for unassisted ventilation with a tracheostomy will follow the local protocol of the participating centers.

F. Sedation

Sedation will be prescribed with a sedation target using RASS or RAMSAY scale re-assessed at least once a day. Sedation will be monitored at least 2 times a day.

A daily cessation of sedation will be performed if there is no contraindication.

The subject's study follow up ends after 28 days after enrollment, even if subject remains on mechanical ventilation. During this 28 days period, for subjects reintubated within 48h after extubation, VFD will not be counted and ventilator protocols will be continued. Subject re-intubated beyond 48h will be considered as weaned for ventilator and ventilator procedures will not be continued.

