4.4 Subgroup Definitions

Forest plots will be used to display results of primary endpoints and total duration of MV within the following subgroups listed below:

- Regions (US vs Europe)
- Study centers
- Gender

All efficacy tables and forest plots displaying primary and tertiary efficacy results will also be presented by treatment arm and for four groups based on subject condition at inclusion:

- Normal lungs
- ARDS
- Chronic Hypercapnia
- Brain injury

Additionally, forest plots to display primary and tertiary efficacy results by spontaneous and passive breathing subjects for the six ventilation and oxygenation variables will be reported:

1) Tidal volume (VT)

- 2) Maximum pressure (Pmax)
- 3) Oxygen saturation measured by pulse oximetry (SpO₂)
- 4) End-tidal partial pressure of carbon dioxide (PetCO₂)
- 5) Respiratory rate (RR) for spontaneous breathing subjects
- 6) Pmax-PEEP for passive ARDS subjects

Study centers will be pooled from largest to smallest until the pooled center had more than 5 subjects in each treatment group.

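### Read literally, total duration of mechanical ventilation counts CPAP/NIV in a failed-extubation gap twice; an overlap rule is missing (minor, secondary endpoint)

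*SAP*

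**What the plan says.** SAP 3.2.2 gives three linked definitions, and protocol 5.2 and the protocol synopsis give the same ones.

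- **Invasive duration.** "Duration of invasive mechanical ventilation: time between intubation and last extubation or death". If re-intubation follows within 48 h of extubation, "the period between extubation and re-intubation is considered as invasive ventilation days".
- **Noninvasive duration.** In the protocol's words, "noninvasive ventilation refers to CPAP or pressure support NIV delivered before intubation or after extubation". The one exclusion is high flow: "High flow therapy is not considered in this calculation".
- **Total duration.** "Total duration of mechanical ventilation: sum of duration of invasive and noninvasive mechanical ventilation".

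The gap rule stops at 48 h. After that, "Subject re-intubated beyond 48h will be considered as weaned from the ventilation".

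Protocol 8.3.1 (part D, on management after extubation) allows the relevant support: "High flow nasal treatment, CPAP, and NIV can be used after extubation". SAP 4.6 (Calculated Variables) gives general rules for durations in days and hours, but none for overlapping ventilation periods.

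On use of the endpoint, SAP 4.4 states: "Forest plots will be used to display results of primary endpoints and total duration of MV within the following subgroups listed below". SAP 10.1 and 10.2 also mark the secondary outcomes tables and the forest plot of key secondary endpoints for production at both interim analyses.

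**The concern.** CPAP or NIV given between a failing extubation and a re-intubation within 48 h is delivered after an extubation, so it meets the noninvasive definition. The same hours lie inside a gap that has already been classed as invasive. A plain sum then counts them twice.

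Two things are at stake. The first is the individual value: for an affected subject, the total is longer than the time on ventilation as the plan itself defines it. The second is reproducibility. Two programmers could derive different totals from the same data, for the only secondary outcome that SAP 4.4 names for subgroup forest plots. Weaning procedures differ by arm (a clinician-run trial in protocol 8.3.2, Quick Wean in 8.3.3), so failed extubation could differ by arm, and the excess with it.

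**Working it through.** The plan states no figure for this endpoint, so there is none to reproduce. The check applies the definitions literally and compares the result with a count in which each hour enters once.

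**Definitions as formulas** (subject re-intubated within 48 h)

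- Invasive = last extubation − first intubation, gap included.
- Noninvasive = CPAP/NIV before first intubation + in the gap + after last extubation.
- Literal total = invasive + noninvasive.
- Union total = invasive + CPAP/NIV before first intubation + CPAP/NIV after last extubation.
- Excess = literal − union = CPAP/NIV hours in the gap.

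**Worked record (constructed).** Intubated at 0 h, extubated at 120 h, re-intubated at 160 h (gap 40 h, with 30 h of NIV), last extubation at 240 h.

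| | No NIV after last extubation | 12 h NIV after last extubation |
|---|---|---|
| Invasive | 240 h | 240 h |
| Noninvasive, literal | 30 h | 30 + 12 = 42 h |
| Literal total | 270 h | 282 h |
| Union total | 240 h | 240 + 12 = 252 h |
| Excess | 30 h | 30 h |

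The 12 h after the last extubation raises both totals correctly. Only the 30 h in the gap is counted twice.

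**Ceiling.** The gap rule applies only within 48 h, so the excess cannot be more than 48 h per failed extubation. With high flow or no support in the gap, it is zero.

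**Effect on an arm mean.** The documents give no re-intubation rate, no share receiving CPAP/NIV in the gap and no hours of such support. All three are assumed here.

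- Gap uniform on 0-48 h: mean 24 h.
- Share of the gap spent on CPAP/NIV uniform on 30-100%, independent of gap length: mean 0.65.
- Mean excess per affected subject: 24 × 0.65 = 15.6 h.
- Mean excess over all subjects = re-intubation rate × share with CPAP/NIV in the gap × 15.6 h.
  - Low: 0.05 × 0.30 × 15.6 = 0.23 h.
  - High: 0.20 × 0.60 × 15.6 = 1.87 h.

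A wider set of assumptions (5-20% re-intubated, 25-75% of those with CPAP/NIV, 6-36 h each) gives 0.05 × 0.25 × 6 = 0.075 h to 0.20 × 0.75 × 36 = 5.4 h, with a middle value of 0.10 × 0.50 × 24 = 1.2 h.

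**Relative size.** Protocol Annex A, Table 10 gives 2-8 days of mechanical ventilation, that is 48-192 h. The 0.23-1.87 h range is then between 0.23/192 = 0.1% and 1.87/48 = 3.9%.

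**Effect on the comparison.** An equal excess in both arms cancels in the difference of means. With 60% on CPAP/NIV in the gap in both arms and re-intubation rates differing by 10 percentage points (also an assumption), the difference in means moves by 0.10 × 0.60 × 15.6 = 0.94 h.

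**The case against.** The strongest reply is that the text can be read without overlap. Classing the gap as invasive may be meant to assign those hours to invasive ventilation alone. With invasive time running to the last extubation, noninvasive time before intubation or after extubation may mean time outside that window. Protocol 8.3.1 points the same way, since after re-intubation within 48 h the ventilator protocol continues and ventilator-free days are not counted. Either reading makes the sum correct. This stands as a plausible account of intent. It does not settle the rule, because the invasive definition specifies the last extubation, the noninvasive definition says only extubation, and the sole stated exclusion is high flow.

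The second reply is that little depends on the point. That also largely stands. This is one of many secondary outcomes. SAP 7.2 provides for medians and a Mann-Whitney test when a variable is non-normal, and these respond less than a mean to extra hours in a few subjects. The SAP 4.4 forest plots of this outcome are subgroup displays, and SAP 7.5 describes subset analyses (there, of the primary efficacy endpoint) as exploratory.

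A reader might also infer that any total longer than the time from intubation to last extubation shows an error. It does not. CPAP/NIV before the first intubation and after the last extubation belongs in the total. Only an excess over the union of the intervals is wrong.

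**Conclusion.** The gap in the definitions is real but minor. Applied as written, the rule counts CPAP/NIV hours between an extubation and a re-intubation within 48 h twice, by up to 48 h per failed extubation. Nothing in the protocol or SAP removes the overlap. The mean shift is about 0.2-1.9 h under the assumed rates, and up to 5.4 h at the extreme of the wider assumptions.

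Three stronger conclusions are tempting, and the documents do not support them.

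- *The trial will double-count these hours.* The documents show a rule that does so when applied literally. They do not show how the variable is programmed.
- *The treatment comparison is biased.* That needs a difference between arms in failed extubation or in gap CPAP/NIV. The different weaning procedures make one possible, but the documents give no rate for either arm.
- *The error is large.* The constructed record above is 30/240 = 12.5% too long, but it assumes a 40 h gap with three quarters of it on NIV. It shows the mechanism and is not a typical subject.

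The co-primary endpoints, alpha, interim boundaries and sample-size reassessment do not use this outcome.

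**What to change.** Add one sentence to SAP 3.2.2 and protocol 5.2, and align the synopsis: *CPAP/NIV time inside an extubation-to-re-intubation interval already counted as invasive ventilation is not added again to noninvasive or total duration.* Alternatively, define total duration as the union of the invasive and noninvasive intervals. If the non-overlapping reading was always intended, the sentence simply records it.

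The cost is that sentence and a small programming rule, best settled before the interim outcomes tables are produced. Whether existing data suffice cannot be verified from the documents. Protocol Table 1 lists NIV, CPAP and high flow as visit-level weaning information, protocol 8.3.4 has the weaning process reported daily, and the CRF is not available here. The sponsor should confirm that CPAP/NIV times are recorded well enough to place them in the gap. Since the whole gap is already counted as invasive, it is enough to tell CPAP/NIV in the gap from CPAP/NIV before the first intubation or after the last extubation.
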